### **4.0 PATIENT SELECTION**

Each of the criteria in the checklist that follows must be met in order for a patient to be considered eligible for this study. Use the checklist to confirm a patient's eligibility. The checklist must be completed for each patient and must be signed and dated by the treating physician.

Patient's Name \_\_\_\_\_

Medical Record # \_\_\_\_\_

Research Nurse /

Study Coordinator Signature: \_\_\_\_\_ Date \_\_\_\_\_

Treating Physician [Print] \_\_\_\_\_

Treating Physician Signature: \_\_\_\_\_ Date \_\_\_\_\_

#### **4.1 Inclusion Criteria**

- \_\_\_\_ 4.1.1 Female with histologically confirmed breast cancer.
- \_\_\_\_ 4.1.2 Patients must have evidence of metastatic disease (non measurable disease is eligible).
- \_\_\_\_ 4.1.3 Radiologically confirmed metastatic brain lesion by MRI.
- \_\_\_\_ 4.1.4 Brain metastases from breast cancer with or without previous treatment. WBRT, STS or surgical resection permitted through progression. Progression must be documented in an at least one lesion untreated by SRS or in any site after surgery or WBRT.
- \_\_\_\_ 4.1.5 Patients must be neurologically stable and with stable dose steroids and anticonvulsants for at least 1 week prior to obtaining the baseline MRI of the brain, and/or at least 1 week prior to beginning study treatment.
- \_\_\_\_ 4.1.6 No presence of uncontrolled systemic disease or tumor related complication which, in opinion of the investigator, might restrict life expectancy to less than 3 months.
- \_\_\_\_ 4.1.7 Patients may not be on any cytotoxic chemotherapy or hormonal treatment for breast cancer during protocol treatment. Trastuzumab is allowed in HER2 positive patients).
- \_\_\_\_ 4.1.8 Subject age  $\geq$  18 years
- \_\_\_\_ 4.1.9 Able to comprehend and willing to sign an Informed Consent Form (ICF)
- \_\_\_\_ 4.1.10 Karnofsky performance status  $\geq$  60

- \_\_\_\_ 4.1.11 No brain radiation therapy > 4 weeks before planned start of protocol treatment.
- \_\_\_\_ 4.1.12 No chemotherapy for > 3 weeks before planned start of protocol treatment.
- \_\_\_\_ 4.1.13 Adequate bone marrow, renal, and hepatic function, per local reference laboratory ranges as follows:
  - \_\_\_\_ 4.1.13.1 Absolute neutrophil count (ANC)  $\geq 1,500/\text{mm}^3$   
ANC= \_\_\_\_\_ Date: \_\_\_\_\_
  - \_\_\_\_ 4.1.13.2 Platelet count  $\geq 100,000/\text{mm}^3$   
Platelets= \_\_\_\_\_ Date: \_\_\_\_\_
  - \_\_\_\_ 4.1.13.3 Hemoglobin  $\geq 9 \text{ g/dL}$   
Hemoglobin= \_\_\_\_\_ Date: \_\_\_\_\_
  - \_\_\_\_ 4.1.13.4 Calculated creatinine clearance (CrCl)  $\geq 30\text{mL/min}$  (Cockcroft-Gault method)
    - Creatinine= \_\_\_\_\_ Date: \_\_\_\_\_
    - Crcl = \_\_\_\_\_ Date: \_\_\_\_\_
  - \_\_\_\_ 4.1.13.5 Patients with normal, mild or moderate hepatic dysfunction are eligible.  
Pugh-Child class= \_\_\_\_\_ Date: \_\_\_\_\_
  - \_\_\_\_ 4.1.13.6 Calcium  $<10.1 \text{ mg/dL}$  (corrected to serum albumin as follows:  
Corrected Calcium =  $(0.8 \times (4 - \text{patient albumin})) + \text{serum Ca}$   
Corrected calcium= \_\_\_\_\_ Date: \_\_\_\_\_
- \_\_\_\_ 4.1.14 Females of child-bearing potential must have a negative pregnancy test at screening and agree to take appropriate precautions to avoid pregnancy (double barrier method of birth control or abstinence) from screening through 3 months after the last dose of treatment
- \_\_\_\_ 4.1.15 Able to undergo MRI evaluation with and without gadolinium contrast

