#### 6.2 **General Concomitant Medications and Supportive Care Guidelines:**

Patient may receive trastuzumab if tumor is HER2 positive. No other cytotoxic or hormonal treatment is allowed while patient is on eribulin mesylate. Three weeks must elapse before beginning eribulin treatment (not protocol entry) after previous cytotoxic chemotherapy.

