#### **11.1.2 Disease Parameters**

Measurable Disease Measurable lesions are defined as brain lesions that can be accurately measured in at least one dimension) as  $\geq 10$  mm by Gd-MRI. All tumor measurements must be recorded in millimeters.

Note: Tumor lesions that are previously treated with stereotactic radiosurgery are not allowed as target lesion.

Non-measurable disease All other lesions including small lesions (longest diameter  $< 10$  mm are considered non-measurable disease.

Note: Cystic lesions that meet the criteria for radiographically defined simple cysts should not be considered as malignant lesions (neither measurable nor non-measurable) since they are, by definition, simple cysts.

‘Cystic lesions’ thought to represent cystic metastases can be considered as measurable lesions if they meet the definition of measurability described above. However, if non-cystic lesions are present in the same patient, these are preferred for selection as target lesions.

Target lesions: All measurable brain metastases  $\geq 10$  mm should be identified as target lesions and recorded and measured at baseline. Target lesions should be selected on the basis of their size (lesions with the longest diameter but in addition should be those that lend themselves to reproducible repeated measurements. It may be the case that, on occasion, the largest lesion does not lend itself to reproducible measurement in which circumstance, the next largest lesion which can be measured reproducible should be selected. A sum of the diameters for all target lesions will be calculated and reported as the baseline sum diameters.

Non-target lesions: All other lesions should be identified as non-target lesions and should also be recorded at baseline. Measurements of these lesions are not required, but the presence, absence, or in rare cases unequivocal progression of each should be noted throughout follow-up.

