##### **Definition of CNS response to eribulin mesylate**

Residual enhancing, non-enhancing, or minimally enhancing tumor:

PR or CR should be confirmed at least 4 weeks after scan showing response.

**Complete Response (CR):** shall be defined as the circumstance when the tumor is no longer seen by neuroimaging, with the patient off all steroids, or on adrenal maintenance only; CR will be coded only if confirmed by a second CT/MR scan performed a minimum of 4 weeks after the initial scan coding a response.

**Partial Response (PR):** Decrease of >50% in the product of two diameters with the patient off all steroids, or on adrenal maintenance only; PR will be coded only if confirmed by a second CT/MR scan performed a minimum of 4 weeks after the initial scan.

**Stable Disease (SD):** shall be defined as the circumstance when the scan shows no change. Patients should be receiving stable or decreasing doses of steroids. This will not need a confirmatory scan.

**Progression (P):** shall be defined as a  $> 25\%$  increase in tumor area (*two diameters*) provided that the patient has not had his/her dose of steroids decreased since the last evaluation period. This will not need a confirmatory scan. A concomitant decrease in steroid dose will rule out a progression designation during the first two months after completion of XRT. (Note: Under exceptional circumstances disease progression may be declared in the absence of an increase in tumor size)

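### As worded, inclusion criterion 4.1.11 bars brain radiation given more than 4 weeks before start and leaves more recent radiation unrestricted; this contradicts 4.1.4 and no other section corrects it

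*Combined protocol and SAP*

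**What the plan says.** Four eligibility and treatment lines in the protocol bear on this.

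- **4.1.11 (brain radiation):** "No brain radiation therapy > 4 weeks before planned start of protocol treatment".
- **4.1.12 (chemotherapy), the next line:** "No chemotherapy for > 3 weeks before planned start of protocol treatment".
- **4.1.4 (prior CNS treatment):** "WBRT, STS or surgical resection permitted through progression", with no time limit, followed by "Progression must be documented in an at least one lesion untreated by SRS or in any site after surgery or WBRT".
- **6.2 (concomitant medication):** "Three weeks must elapse before beginning eribulin treatment (not protocol entry) after previous cytotoxic chemotherapy". Radiation is not mentioned there.

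The criteria form a checklist that the treating physician signs and dates. Section 4.0 makes all of them binding: "Each of the criteria in the checklist that follows must be met in order for a patient to be considered eligible for this study".

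Two further provisions touch on radiation. Section 11.1.2 states: "Tumor lesions that are previously treated with stereotactic radiosurgery are not allowed as target lesion". The definition of CNS response in 11.1.4 adds: "A concomitant decrease in steroid dose will rule out a progression designation during the first two months after completion of XRT".

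The primary endpoint (13.1) is the proportion without CNS progression at 3 months in a single arm. Section 13.0 calls 8 or more of 20 positive, against a rate of 15% that would not be meaningful.

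**The concern.** A criterion of this kind normally keeps out patients whose brain disease was treated so recently that the effect of that treatment cannot be separated from the effect of the study drug. As worded, 4.1.11 does the reverse: it removes patients with older radiation and places no bar on recent radiation.

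Two things are at stake. The first is who is eligible. Patients who progressed after brain radiation given more than 4 weeks earlier meet 4.1.4 and fail 4.1.11. Staff must either turn them away or silently reinterpret a signed line. If staff apply the probable intent, those patients become eligibility deviations on the text as it stands.

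The second is interpretation. The trial has no control arm, the benchmark is a fixed 15%, and the analysis makes no adjustment for time since radiation. Any CNS control left over from recent radiation would be counted as an eribulin success.

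**Working it through.** **Step 1. The lines side by side.**

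| Line | What it does as worded | Restated elsewhere? |
|---|---|---|
| 4.1.11, brain radiation | Forbids radiation more than 4 weeks before start; silent on radiation within 4 weeks | No |
| 4.1.12, chemotherapy | The word *for* makes it a drug-free interval of more than 3 weeks | Yes, in 6.2, as time that must elapse |
| 4.1.4, prior CNS treatment | Admits earlier WBRT, radiosurgery or surgery with documented progression, at any time | – |

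**Step 2. Apply 4.1.4 and 4.1.11 together, as section 4.0 requires.**

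- Never irradiated: 4.1.11 has no effect.
- Irradiated more than 4 weeks before start, with documented progression: meets 4.1.4, fails 4.1.11.
- Irradiated only within the last 4 weeks, with the progression that 4.1.4 requires: meets both.

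Of the previously irradiated patients whom 4.1.4 admits, literal 4.1.11 keeps only the recently treated ones. The exclusion criteria in 4.2 say nothing on radiation timing, so nothing there restores the balance.

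**Step 3. How recent radiation could reach the endpoint.** After WBRT, 4.1.4 requires progression at some site. After radiosurgery, it requires progression in at least one lesion that was not treated that way, and 11.1.2 keeps radiosurgery-treated lesions from being targets. Some exposure remains. Lesions treated with WBRT may still be targets. The baseline MRI may also be up to 30 days before therapy (10.1, 11.1), so radiosurgery to one lesion could fall between that scan and the first dose while another, untreated lesion satisfies 4.1.4.

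**Step 4. The plan's own figure.** Section 13.0 gives a 95% CI of 18.5–61.5% at 8 of 20. The Wald formula reproduces it:

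0.40 ± 1.96 × √(0.40 × 0.60 / 20) = 0.40 ± 0.215, or 18.5% to 61.5%.

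The exact chance of meeting the rule at the 15% rate is P(Bin(20, 0.15) ≥ 8) = 0.0059, or 0.6%.

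**Step 5. Illustration of the possible bias.** Two inputs are assumed, and neither is in the documents: *m*, the number of the 20 who were recently irradiated, and *r*, their 3-month CNS PFS rate, taken as 40–70%. All other patients are held at 15%, which represents an inactive drug. Then

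P(success) = P(X + Y ≥ 8), with X ~ Bin(m, r) and Y ~ Bin(20 − m, 0.15).

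| m of 20 | Expected successes, r = 0.40 to 0.70 | P(≥ 8 of 20), r = 0.40 | P(≥ 8 of 20), r = 0.70 |
|---|---|---|---|
| 0 | 3.0 | 0.6% | 0.6% |
| 2 | 3.5 to 4.1 | 1.3% | 2.6% |
| 5 | 4.25 to 5.75 | 3.9% | 15% |
| 10 | 5.5 to 8.5 | 15% | 71% |

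Expected successes are m·r + (20 − m) × 0.15; for example, 5 × 0.70 + 15 × 0.15 = 5.75.

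**The case against.** The strongest reply is that this is a dropped word whose meaning any reader can recover. Line 4.1.12 has the same form with *for* included. Inserting *for* in 4.1.11 gives an ordinary radiation-free interval, and the literal reading nearly defeats 4.1.4. The trial is run by one cancer center with two collaborating institutions, and registration goes through one unit (5.0), so divergent readings are less likely than in a large network. This stands as an account of the probable intent. It does not make the line correct: it is a binding, signed criterion, and no section confirms either its direction or its interval.

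A reader might also infer that recent radiation would drive the 3-month CNS PFS, or that the design deliberately selects recently irradiated patients. The documents support neither. The parallel line points to a slip. A patient given WBRT within 4 weeks must already have progressed to meet 4.1.4, and nothing in the documents shows that such patients would have 40–70% CNS control. New lesions and unequivocal progression still count as progression (11.1.4.1). The 71% figure needs half the trial to be recently irradiated and a 70% rate among them. With 2 of 20, the chance of a false positive stays below 3%.

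**Conclusion.** Criterion 4.1.11 is wrong as written and contradicts 4.1.4. That conclusion rests on the text alone and needs no assumption. The probable cause is a missing word, but the protocol does not settle it, because 6.2 restates the interval only for chemotherapy.

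The effect on the primary endpoint is a possible bias of unknown size. The figures of 1.3–2.6%, 3.9–15% and 15–71%, against 0.6% with no recently irradiated patients, show only how sensitive a single-arm rule could be. They rest on an assumed share, an assumed rate, and an inactive drug in everyone else. The progression requirement in 4.1.4 and the bar on radiosurgery-treated target lesions both narrow the route. The documents also do not say how many patients admitted by 4.1.4 the literal line would exclude.

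**What to change.** The sponsor should reconcile 4.1.11 with 4.1.4 and confirm the intended direction and length of the interval. The line should then be reworded so that it has only one reading, and the signed eligibility checklist corrected to match. The choice of interval is the sponsor's; none is proposed here.

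If patients have already been enrolled, their radiation dates should be checked against the clarified rule.

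The cost is one line in the protocol and the same line in the checklist. It needs no extra patients or procedures, and the sample size, the 8-of-20 rule and the analysis stay the same.

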## 4.2 Exclusion Criteria

- \_\_\_\_ 4.2.1 Patients with the presence of an active infection, abscess or fistula
- \_\_\_\_ 4.2.2 Known leptomeningeal disease or CNS midline shifts.
- \_\_\_\_ 4.2.3 Any evidence of severe or uncontrolled systemic disease such as clinically significant cardiovascular, pulmonary, hepatic, renal or metabolic disease.

- \_\_\_\_\_ 4.2.4 Severe conduction abnormality including significant QTc prolongation >450ms.
- \_\_\_\_\_ 4.2.5 Patients with grade 3/4 peripheral neuropathy.
- \_\_\_\_\_ 4.2.6 Patients with pacemaker or an ICD devices.
- \_\_\_\_\_ 4.2.7 Previous treatment with eribulin mesylate.

#### 4.3 **Inclusion of Women and Minorities**

Women of all races and ethnic groups are eligible for this trial.

### 5.0 **REGISTRATION**

All subjects who have been consented are to be registered in the OnCore Database. All subjects will be registered through Seidman Cancer Center CTU and will be assigned a study number by the study coordinator at [contact].

### 6.0 **TREATMENT PLAN**

#### 6.1 **Agent Administration: Eribulin**

TABLE 1:TREATMENT REGIMEN DESCRIPTION					
Agent	Pre-medicate at the Treating Physician's Discretion	Dose	Route	Schedule	Cycle Length
Eribulin mesylate	Zofran 8mg oral Decadron 8mg oral	1.4 mg/m  (see section 7.1 for details)	IV over 2-5 Min	Days 1 & 8 of each 21 day cycle	21 days

#### 6.2 **General Concomitant Medications and Supportive Care Guidelines:**

Patient may receive trastuzumab if tumor is HER2 positive. No other cytotoxic or hormonal treatment is allowed while patient is on eribulin mesylate. Three weeks must elapse before beginning eribulin treatment (not protocol entry) after previous cytotoxic chemotherapy.

### 7.0 **DOSING DELAYS / DOSE MODIFICATIONS:**

#### 7.1. **Dosing**

The recommended starting dose of eribulin mesylate is 1.4 mg/m^2 administered intravenously over 2 to 5 minutes on Days 1 and 8 of a 21-day cycle. No calculation of Child-Pugh score is necessary for those without known hepatic impairment from hepatitis, cirrhosis or liver metastases.

**7.1.1** The recommended dose of eribulin mesylate in patients with mild hepatic impairment (Child-Pugh A) is 1.1 mg/m^2 administered intravenously over 2 to 5 minutes on Days 1 and 8 of a 21-day cycle.

**7.1.2** The recommended dose of eribulin mesylate in patients with moderate hepatic impairment (Child-Pugh B) is 0.7 mg/m^2 administered intravenously over 2 to 5 minutes on Days 1 and 8 of a 21-day cycle.

**7.1.3** The recommended dose of eribulin mesylate in patients with moderate renal impairment (creatinine clearance of 30-50 mL/min) is 1.1 mg/m^2 administered intravenously over 2 to 5 minutes on Days 1 and 8 of a 21-day cycle.

## **7.2 Dose Modification**

### **Assess for peripheral neuropathy and obtain complete blood cell counts prior to each dose.**

It is not necessary to recalculate the BSA (Body Surface Area) for each treatment if the patient's weight has not changed by more than 10% from baseline. Prior to each administration of study drug, the nurse recalculates the BSA, the daily dose and the total dose of all chemotherapy treatment drug(s). A 5% variance rule is utilized between the ordered dose and the recalculated dose. As long as the recalculated dose is within 5%, it is acceptable to proceed.

#### **Recommended dose delays**

##### **Do not administer eribulin mesylate on Day 1 or Day 8 for any of the following:**

ANC < 1,000/mm^3

Platelets < 75,000/mm^3

Grade 3 or 4 non-hematological toxicities.

#### **The Day 8 dose may be delayed for a maximum of 1 week.**

If toxicities do not resolve or improve to  $\leq$  Grade 2 severity by Day 15, omit the dose.

If toxicities resolve or improve to  $\leq$  Grade 2 severity by Day 15, administer eribulin mesylate at a reduced dose and initiate the next cycle no sooner than 2 weeks later.

Recommended dose reductions: If a dose has been delayed for toxicity and toxicities have recovered to Grade 2 severity or less, resume eribulin mesylate at a reduced dose as set out in Table 1. Do not re-escalate Eribulin dose after it has been reduced.

Table 2: Recommended Dose Reductions Event Description	Recommended Eribulin Dose
Permanently reduce the 1.4 mg/m^2 eribulin mesylate dose for any of the following:	1.1 mg/m 
ANC <500/mm  for >7 days	
ANC <1,000 /mm  with fever or infection	
Platelets <25,000/mm 	
Platelets <50,000/mm  requiring transfusion	
Non-hematologic Grade 3 or 4 toxicities	
Omission or delay of Day 8 Eribulin dose in previous cycle for toxicity	
Occurrence of any event requiring permanent dose reduction while receiving 1.1 mg/m^2	0.7 mg/m 
Occurrence of any event requiring permanent dose reduction while receiving 0.7 mg/m^2	Discontinue eribulin mesylate

## 8.0 ADVERSE EVENTS: LIST AND REPORTING REQUIREMENTS

The following is a list of AEs (Section 8.1) and the reporting requirements associated with observed AEs (Sections 8.3 and 8.4).

The clinical course of each event will be followed until resolution, stabilization, or until it has been determined that the study treatment or participation is not the cause.

Serious adverse events that are still ongoing at the end of the study period will necessitate follow-up to determine the final outcome. Any serious adverse event that occurs after the study period and is considered to be possibly related to the study treatment or study participation will be recorded and reported immediately.

### 8.1 Adverse Events and Potential Risks

#### 8.1.1 Adverse Effects related to eribulin mesylate

#### 8.1.2 Neutropenia

- Monitor complete blood counts prior to each dose, and increase the frequency of monitoring in patients who develop Grade 3 or 4 cytopenias. Delay administration and reduce subsequent doses in patients who experience febrile neutropenia or Grade 4 neutropenia lasting longer than 7 days.
- Severe neutropenia (ANC <500/mm^3) lasting more than 1 week occurred in 12% (62/503) of patients. Patients with elevated liver enzymes >3 × ULN and bilirubin >1.5 × ULN experienced a higher incidence of Grade 4 neutropenia and febrile neutropenia than patients with normal levels.
- Grade 3 and Grade 4 neutropenia occurred in 28% and 29%, respectively, of patients who received eribulin. Febrile neutropenia occurred in 5% of patients and two patients (0.4%) died from complications.

### **8.1.3 Peripheral Neuropathy**

- Grade 3 peripheral neuropathy occurred in 8% of patients, and Grade 4 in 0.4% of patients who received eribulin. Delay administration of eribulin until resolution to Grade 2 or less.
- Neuropathy lasting more than 1 year occurred in 5% of patients. Twenty-two percent of patients developed a new or worsening neuropathy that had not recovered within a median follow-up duration of 269 days (range 25-662 days)
- Peripheral neuropathy (5%) was the most common adverse reaction resulting in discontinuation

### **8.1.4 Pregnancy Category D**

- Eribulin is expected to cause fetal harm when administered to a pregnant woman and patients should be advised of these risks

### **8.1.5 QT Prolongation**

- In an uncontrolled ECG study in 26 patients, QT prolongation was observed on Day 8, independent of eribulin concentration, with no prolongation on Day 1. ECG monitoring is recommended for patients with congestive heart failure; bradyarrhythmias; concomitant use of drugs that prolong QT interval, including Class Ia and III antiarrhythmics; and electrolyte abnormalities.
- Correct hypokalemia or hypomagnesaemia prior to initiating eribulin mesylate and monitor electrolytes periodically during therapy. Avoid in patients with congenital long QT syndrome.

### **8.1.6 Hepatic and Renal Impairment**

For patients with mild (Child-Pugh A) or moderate (Child-Pugh B) hepatic and/or moderate (CrCl 30-50 mL/min) renal impairment, a reduction in starting dose is recommended.

## **8.2 MRI**

### **8.2.1 Adverse Events related to Magnetic Resonance Imaging (MRI)**

A known risk related to MRI examinations is that the MRI magnet could attract certain kinds of metal that may cause injury to the patient. In order to avoid that, patients will be screened for any hazardous metal object that they may have or is implanted inside their body which includes pacemakers, intracranial aneurysm clips, heart valve prostheses and other implanted devices that are not compatible with MRI. Although there is no risk from ionizing radiation with MRI, subjects will be exposed to strong magnetic fields and radio waves, neither of which are associated with any known detrimental health effects.

For MR perfusion imaging we will use a contrast agent, gadolinium. This agent is approved by the FDA and commercially available. There is a risk of an allergic or nephrogenic systemic fibrosis (NSF) reaction. Allergic (anaphylactic) reactions to gadolinium contrast medium have occurred but are

extremely rare. These severe reactions occur in about 1 in every 10,000 people who have gadolinium. NSF has not been reported in patients with normal kidney function. Patients at greatest risk for developing NSF after receiving gadolinium are those with impaired elimination of the drug, including patients with acute kidney injury (AKI) or chronic, severe kidney disease (with a glomerular filtration rate or GFR < 30 mL/min/1.73m^2). Higher than recommended doses or repeat doses of GBCAs also appear to increase the risk for NSF.

Generally, an injection of 10-20 ml IV of gadolinium contrast agent will be used, provided that the subject has no known reaction to contrast agents used in previous MRI scans. As with all such injections, bleeding, bruising, dizziness, fainting or infection may occur. Also, the injection may be painful but the discomfort should be brief and efforts will be made to minimize the pain.

The MRI scanner makes a loud buzzing sound during the exam that could affect a patient's hearing. In order to protect patient from this sound, they will be provided earplugs during the exam. There might also be some claustrophobia-related discomfort involved with being required to lie still in a small space. If this occurs, patients can signal the technologist attending the MRI who will terminate imaging. The subject will be removed from the MRI machine and regarded as being withdrawn from the study, with the exception of following the patient for any sign of adverse event to the injected study drug.

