### **3.4. Duration of Therapy**

In the absence of treatment delays due to adverse events, treatment may continue on study until one of the following criteria applies:

- Systemic or CNS disease progression,
- Intercurrent illness that prevents further administration of treatment,
- The investigator considers it, for safety reasons, to be in the best interest of the patient.
- Unacceptable treatment related toxicity, NCI CTC AE version 4.0. Grade 3 or 4 that fails to recover to baseline or < Grade 2 in the absence of treatment within 4 weeks
- General or specific changes in the patient's condition render the patient unacceptable for further treatment in the judgment of the investigator,
- Patient decision to withdraw from treatment (partial consent) or from the study (full consent),
- Pregnancy during the course of the study
- Death

The date and reason for discontinuation must be documented. Every effort should be made to complete the appropriate assessments.

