### **3.5 Duration of Follow Up:**

**30-Day Follow-Up:** Patients will be followed *for toxicity* for 30 days after treatment has been discontinued or until death, whichever occurs first.

**Long term Follow-Up:** Patients will be followed *for survival* every 3 months until death after discontinuation of study medications.

The clinical course of each event will be followed until resolution, stabilization, or until it has been determined that the study treatment or participation is not the cause.

Serious adverse events that are still ongoing at the end of the study period will necessitate follow-up to determine the final outcome. Any serious adverse event that occurs after the study period and is considered to be possibly related to the study treatment or study participation will be recorded and reported immediately.

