### **3.6 Replacement of Subjects**

Subjects who do not obtain the two MRI scans (baseline and 12 weeks) will be considered not evaluable for response and will be replaced.

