### **Evaluability**

To be evaluable for inclusion in the primary objective and secondary objectives, patients must have baseline and week 12 MRI.

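### Section 8.2.1 treats one MRI stopped for claustrophobia as withdrawal from the study, which contradicts sections 3.4, 3.5 and 3.6 and can cut off evaluability and follow-up without need

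*Combined protocol and SAP*

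**What the plan says.** Section 8.2.1 describes claustrophobia as a possible discomfort of MRI. If it occurs, "patients can signal the technologist attending the MRI who will terminate imaging". The patient is then "regarded as being withdrawn from the study, with the exception of following the patient for any sign of adverse event to the injected study drug". The rule names no particular scan and mentions no second attempt.

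Other sections deal with the same situation differently:

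- **Section 3.4** lists the grounds for ending therapy, introduced by "treatment may continue on study until one of the following criteria applies". An incomplete scan is not among them. Withdrawal appears as "Patient decision to withdraw from treatment (partial consent) or from the study (full consent"), so leaving treatment and leaving the study are separate, and both are the patient's choice. The section adds: "Every effort should be made to complete the appropriate assessments".
- **Section 3.5** follows patients for survival "every 3 months until death after discontinuation of study medications", with no exception for a stopped scan.
- **Section 3.6** covers a missing scan: "Subjects who do not obtain the two MRI scans (baseline and 12 weeks) will be considered not evaluable for response and will be replaced". It does not call such patients withdrawn.
- **Section 13.0, Evaluability**, says that for the primary and secondary objectives "patients must have baseline and week 12 MRI".
- **Section 10.1.1** allows ±7 days around the 3-month scans.

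**The concern.** A site cannot follow all of these sections at once. If it follows section 8.2.1, a single interrupted scan moves the patient from a missing assessment, which the plan already handles, to loss from the study, which it does not need.

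Two things are at stake. A week-12 scan that might have been completed a few days later is not obtained, and the patient drops out of the evaluable set. A patient who stops a later scan, after a complete week-12 assessment, loses the rest of her progression and survival follow-up, although nothing in sections 3.4 to 3.6 calls for that. The adverse-event follow-up that is kept is also unclear. The text around the rule is about injected gadolinium, while the study drug is eribulin.

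**Working it through.** **1. What section 8.2.1 adds, by type of scan**

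| Scan stopped | Without the rule | With the rule as written |
|---|---|---|
| Week 12 | The scan can still be obtained within ±7 days (10.1.1). If it is not, the patient is non-evaluable and replaced (3.6, Evaluability). | She is already withdrawn, so the window cannot be used and she becomes non-evaluable. Survival follow-up also ends. |
| Confirmatory scan, at least 4 weeks after a response (11.1.4) | The scan could be rescheduled. Follow-up continues. | Confirmation is not obtained and the response may go uncoded. Follow-up ends. |
| Week 24 or later | 3-month status is already recorded. Progression and survival follow-up continue. | CNS, systemic and survival follow-up end. She is censored at that point. |

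In the week-12 row, exclusion from the analysis comes from section 3.6 and the Evaluability paragraph. Section 8.2.1 contributes by blocking the repeat that could have avoided it. In the other two rows the loss of follow-up comes from section 8.2.1 alone.

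**2. How many patients**

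The documents give no rate of stopped scans. As an assumption, take 1–5% per scan. Take 20 patients scanned at week 12, a fixed share going on to each later 12-weekly scan, and three rounds. The share is either the expected 35% or 50%, the top of the range cited under Sample size, carried forward as a further assumption.

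- 35%: 20 + 7 + 2.45 = 29.45 scans. × 1–5% = 0.3 to 1.5 patients.
- 50%: 20 + 10 + 5 = 35 scans. × 1–5% = 0.35 to 1.75 patients.
- After week 12 only: 9.45 scans give 0.1 to 0.5 patients, and 15 scans give 0.15 to 0.75.

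Confirmatory scans would add a few. Criterion 4.1.15, which requires the ability to undergo MRI, would lower the count.

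**3. Direction of any bias in the 3-month result**

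The plan's own figure reproduces: 8/20 = 40%, and 0.40 ± 1.96 × √(0.40 × 0.60/20) = 0.40 ± 0.215, or 18.5–61.5%. For the rule of at least 8 of 20, the exact binomial probability of success is 0.0059 at a true rate of 15% and 39.9% at 35%.

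Let w₀ and w₁ be the assumed proportions of non-progressors and progressors lost and replaced. The rate among evaluable patients is p′ = p(1 − w₀) / [p(1 − w₀) + (1 − p)(1 − w₁)].

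- Equal loss (w₀ = w₁ = 10%): p′ = p, so there is no bias.
- Only progressors lost (w₁ = 10%): 0.15/(0.15 + 0.765) = 16.4%. Type I error rises from 0.0059 to 0.0102.
- Only non-progressors lost (w₀ = 10%): 0.135/(0.135 + 0.85) = 13.7%. The 35% rate becomes 0.315/(0.315 + 0.65) = 32.6%, and power falls from 39.9% to 31.4%.

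These show direction only. A 10% loss is above the 1–5% assumed in step 2, and section 8.2.1 accounts only for patients whose repeat scan it blocks.

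**The case against.** The best reply is that the rule changes little. A patient who never completes week 12 is already outside both the primary and the secondary analyses under the Evaluability paragraph. Section 8.2.1 sits in a description of MRI risks, does not mention eribulin, and may never have been meant to govern study conduct. Section 3.5 makes no exception for full withdrawal of consent either, so it can be read as a general default. Whatever agent is meant, sections 3.5, 8.3 and 8.5 already provide 30-day safety follow-up.

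Much of this stands, and it limits the size of the point. The contradiction remains: study withdrawal is the fuller of the two kinds in section 3.4, and section 8.2.1 says that only adverse-event follow-up survives it.

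A reader might infer more than the documents support:

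- **That the loss is likely to be informative.** The trigger is claustrophobia, which may have nothing to do with prognosis. A link through neurological decline is possible but not documented. New or worsening tumor-related neurologic symptoms already count as progression in section 11.1.4.1, without a scan.
- **That each such patient shifts any proportion by 1/20, or 5 percentage points.** Before week 12 she is replaced, so the denominator stays at 20 evaluable. After week 12 her 3-month status and clinical benefit are already recorded.
- **That these patients vanish from overall survival.** A patient evaluable at week 12 and withdrawn at week 24 would ordinarily contribute about 24 weeks to the Kaplan-Meier curve and then be censored.

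**Conclusion.** The point holds as a contradiction in operative text, with a small expected effect. Section 8.2.1 conflicts with sections 3.4, 3.5 and 3.6. Read literally, it prevents use of the week-12 window and ends progression and survival follow-up after a stopped confirmatory or later scan.

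The number affected is probably no more than one or two patients, on assumed stopping rates that the documents neither support nor exclude. The bias may be nil or run either way. Because follow-up stops, the trial could not find out which, and section 13.1 gives no censoring rule for overall survival. That study treatment also stops is the natural reading of withdrawal from the study, but section 8.2.1 does not say so. It should be corrected because the conflict is plain and the correction cheap, not because it threatens the primary result.

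**What to change.** Replace the last sentence of section 8.2.1 with wording such as: *An incomplete scan is not in itself withdrawal from the study. Unless she withdraws consent, the patient stays in follow-up for progression (section 11.1.4, Response Criteria) and survival (section 3.5). Her evaluability is decided under section 3.6 and the Evaluability paragraph, by whether the scan is obtained within the window of section 10.1.1.* Section 13.1 should say how patients who do leave early are censored.

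The sponsor should also reconcile three matters, on which this review proposes no clinical rule:

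- whether a stopped scan has any bearing on treatment, given that section 3.4 does not list it;
- whether and how a scan is re-attempted, given the caution in section 8.2.1 about repeat gadolinium doses and the eligibility of patients with creatinine clearance from 30 mL/min (4.1.13.4);
- which agent the retained adverse-event follow-up refers to, so that it agrees with sections 3.5, 8.3 and 8.5.

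The cost is a wording change, an occasional rescheduled scan, and survival contacts that section 3.5 already plans. One limit remains: a patient who never obtains the week-12 scan would be followed for survival but would stay outside the analysis while the Evaluability paragraph stands.
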